12.1.4.2 Eribulin plasma levels

Eribulin plasma levels will be determined using a validated LC/MS/MS analytical assay also available in the Analytical Pharmacology Core Facility (APCF). Briefly, following reversed phase LC separation, eribulin and internal standard (ER-076349) will be monitored by tandem MS with electrospray positive ionization operating at a capillary voltage of 2.9 kV and a cone voltage of 58 V. The detector is set to monitor the parent/daughter transitions [MH⁺] for E (m/z 730 to m/z 712) and IS (m/z 732 to m/z 681). The lower limit of quantitation of the assay is 0.1ng/ml from a 200 μ l aliquot of plasma.

12.1.5 Pharmacokinetic data analysis

Non-compartmental PK analyses of everolimus will be performed using statistical moment theory and according to the rule of linear trapezoids and statistical moment theory. Everolimus PK parameters (C_{max}, C_{trough}, AUC, CL/F, t_{1/2}) will be determined for each individual and a two-stage approach will be used to describe the study population PK.

Compartmental analyses will be performed for eribulin data using ADAPT II (USC Biomedical Simulations Resource, Los Angeles, CA). Secondary pharmacokinetic parameters (e.g. CL_{sys}, V_d, t_{1/2}'s, AUC_{0- ∞}) will be determined for each individual and a two-stage approach will be used to describe the study population pharmacokinetics. Population means and standard deviations will be compared to values obtained from patients treated on trials of single agent eribulin.

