Everolimus has been evaluated in a number of clinical trials including in patients with solid tumors and MBC.²⁸⁻³⁰ In patients with advanced solid tumors, oral everolimus is rapidly absorbed with a median time to peak concentration of 1-2 hours post-dose. The steady-state AUC_{0-τ} (area under the plasma concentration-time curve from time zero to the last measurable concentration) is dose-proportional over the dose range of 5-70mg in a weekly regimen and 5-10mg in a daily regimen. In a randomized, double-blind, multicenter phase III study of everolimus and exemestane versus placebo and exemestane for estrogen receptor (ER)-positive MBC, 724 patients were randomized in a 2:1 ratio to receive either 10mg daily everolimus (N=485) or matching placebo (N=239) in addition to open-label 25mg daily exemestane. The study demonstrated a statistically significant clinical benefit of the everolimus and exemestane over placebo and exemestane by a 2.4-fold increase in median progression-free-survival (PFS) (6.93 months versus 2.83 months), resulting in a 57% risk-reduction of progression or death. Objective response was observed in 9.5% of patients in the everolimus and exemestane arm versus 0.4% in the placebo and exemestane arm (p<0.0001). Furthermore, the CBR for patients receiving everolimus and exemestane was 33.4% versus 18% in patients receiving placebo and exemestane (p<0.0001.) The most common grade 3-4 AEs in the everolimus and exemestane group versus the placebo and exemestane group were stomatitis (8% versus 1%), anemia (6%

versus <1%), dyspnea (4% versus 1%), hyperglycemia (4% versus <1%), fatigue (4% versus 1%), and pneumonitis (3% versus 0%).³⁰

Approximately 35,982 cancer patients have been treated with everolimus as of 31-Mar-2014:

- 19,668 patients in Novartis-sponsored clinical trials
- 2,394 patients in the individual patient supply program
- More than 13,930 patients in investigator-sponsored studies.

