11.1 Design

11.1.1 Phase I portion

The Phase I portion of this study will use the toxicity equivalence range (TEQR) design of Blanchard and Longmate [35] to evaluate select dose levels of the everolimus in combination with eribulin and to determine the RP2D. In this implementation of the TEQR design, we define the target equivalence range of the DLT rate as 0.20-0.35. DLT rate levels of 0.51 or higher will be considered too toxic and doses that achieve that level will not be revisited. The dose escalation de-escalation rules will be the following. If the rate of participants that experience a DLT is below 0.20 we will escalate, if the rate is above 0.35 we will de-escalate and if it is between 0.20-0.35 we will stay at the current dose. Participants will enter the protocol in cohorts of 3. The starting dose will be dose level 1. This study will end when 12 research participants are studied at a single dose level with a toxicity level below 0.51. Further we also implement the additional rules: 1) terminate the trial if dose level 1 is too toxic, and 2) if the current dose is safe but based on the data the next dose is deemed too toxic, stay at the current dose. The RP2D will be the dose closest to target of 0.25 below 0.51 based on isotonic regression. The dose schedule is provided in Table 11.1 below.

The PMT team for protocol 14036 reviewed the data: dose level 2 was closed after 2 of 3 evaluable participants experienced DLTs an observed rate of 67%; dose level 1, we saw 4 DLTs in 8 evaluable participants giving an observed DLT rate of 50% on this dose. Our equivalence range for DLT rate for this trial is 20-35%, our observed rate of 50% is above 35% so we plan to de-escalate. Two participants experienced grade 4 neutrophil count decrease and 2 experienced mucositis (1 grade 3 DLT, 1 participant received 71% of Everolimus due to grade 2 which is a DLT). Thus, the team decided to amend the protocol to allow for two new dose levels at a lower dose of Eribulin, and start the next cohort of patients at dose level B1.

Table 11.1 Dosing Schedule: cycle length is 21 days

Dose level A	Everolimus (oral)	Eribulin (intravenous)
A-1	2.5mg daily (day 1 to 21)	1.4mg/m ² on days 1, 8
A1	5mg daily (day 1 to 21)	1.4mg/m ² on days 1,8
A2	7.5mg daily (day 1 to 21)	1.4mg/m ² on days 1,8
A3	10mg daily (day 1 to 21)	1.4mg/m ² on days 1, 8

Dose level B	Everolimus (oral)	Eribulin (intravenous)
B1	5mg daily (day 1 to 21)	1.1mg/m ² on days 1,8

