12.1.3 Sampling Schedule

Everolimus Sample Collection

PK Time Point	Sample Type	Cycle	Day	Collection time 24-hour clock)
WB1	Whole Blood	1	D1 +/- 10 min	00:00
WB2	Whole Blood	1	D1 +/- 10 min	01:00
WB3	Whole Blood	1	D1 +/- 10 min	02:00

WB4	Whole Blood	1	D1 +/- 10 min	04:00
WB5	Whole Blood	1	D1 +/- 10 min	06:00
WB6	Whole Blood	1	D2 +/- 2 hours	24:00
WB7	Whole Blood	2	D1 +/- 10 min	00:00
WB8	Whole Blood	2	D1 +/- 10 min	01:00
WB9	Whole Blood	2	D1 +/- 10 min	02:00
WB10	Whole Blood	2	D1 +/- 10 min	04:00
WB11	Whole Blood	2	D1 +/- 10 min	06:00
WB10	Whole Blood	2	D2 +/- 2 hours	24:00

Eribulin Sample Collection

PK Time Point	Sample Type	Cycle	Day	Sample Description	Collection time 24-hour clock)
P1	Plasma	2	D1	Pre	00:00
P2	Plasma	2	D1	End of infusion	00:05
P3	Plasma	2	D1	10 min	00:10
P4	Plasma	2	D1	15 min	00:15
P5	Plasma	2	D1	30 min	00:30
P6	Plasma	2	D1	1 hr +/- 10 min	01:00
P7	Plasma	2	D1	2 hr +/- 10 min	02:00
P8	Plasma	2	D1	4 hr +/- 10 min	04:00
P9	Plasma	2	D1	6 hr +/- 10 min	06:00
P10	Plasma	2	D2	24 hr +/- 2 hours	24:00
P11	Plasma	2	D3	48 hr +/- 3 hours	48:00
P12	Plasma	2	D4	72 hr +/- 3 hours	72:00
P13	Plasma	2	D8	167 hr +/- 3 hours	167:00

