12.1.4 Analytical methods

12.1.4.1 Everolimus blood concentrations

Everolimus blood concentrations will be determined in all samples in the Analytical Pharmacology Core Facility (APCF) at the City of Hope using a validated LC-MS/MS method. Briefly, following sample clean-up and LC separation from interfering substances in whole blood, a Micromass Quattro Ultima triple quadrupole mass spectrometer operating in positive ion mode is used to detect everolimus according to the mass transition of m/z 975.5 → 908.5 with tacrolimus (m/z 821.5 → 768.5) as the internal standard. The limit of quantitation for everolimus in whole blood is 0.25ng/ml.

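### Linear trapezoids across the unsampled 6 to 24 h interval will usually overstate everolimus AUC; linear-up/log-down is usually closer and needs no new samples

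*Combined protocol and SAP*

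**What the plan says.** Section 12.1.5 makes the everolimus analysis non-compartmental, with areas computed "according to the rule of linear trapezoids and statistical moment theory". It gives no separate rule for the declining part of the curve. The dependent quantities are listed next: "Everolimus PK parameters (C_{max}, C_{trough}, AUC, CL/F, t_{1/2}) will be determined for each individual". The section names AUC to infinity for eribulin but gives no interval for the everolimus AUC or for the AUC behind CL/F.

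Section 12.1.3 schedules everolimus whole blood at 0, 1, 2, 4, 6 and 24 h in cycles 1 and 2. The rows either side of the gap in cycle 1 are "WB5 Whole Blood 1 D1 +/- 10 min 06:00" and "WB6 Whole Blood 1 D2 +/- 2 hours 24:00". Cycle 2 has the same gap after "WB11 Whole Blood 2 D1 +/- 10 min 06:00".

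Three other passages matter:
- **Time to peak.** Section 1.2.2 says that in patients with advanced solid tumors "oral everolimus is rapidly absorbed with a median time to peak concentration of 1-2 hours post-dose".
- **Dosing.** Table 11.1 has everolimus given every day of the 21-day cycle, so the dosing interval is 24 h.
- **Assay limit.** Section 12.1.4.1: "The limit of quantitation for everolimus in whole blood is 0.25ng/ml".

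PK parameters are a secondary endpoint (Section 3.2), and Section 11.3 summarizes them descriptively.

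**The concern.** With a median peak at 1 to 2 h, the 6 to 24 h interval lies on the falling limb. A straight line between two points of a convex decline lies above the curve, so the linear rule adds area there. The line spans 18 h (16 to 20 h with the window on the 24 h draw), so the excess need not be small.

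The excess grows with the fall from 6 to 24 h. It therefore differs between patients, and between the first-dose profile and the cycle 2 profile. AUC and CL/F describe everolimus exposure in the combination, and a method error that varies with the shape of the curve blurs both.

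**Working it through.** The plan states no everolimus AUC, clearance, half-life or expected concentration, so there is no figure to reproduce. The sampling times, the integration rule and the 1 to 2 h peak come from the documents. Every curve shape below is an assumption.

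**1. The 6 to 24 h segment alone.** Let R = C6/C24, with a mono-exponential fall. Per unit of C6:
- linear area = 18 × (1 + 1/R)/2
- true (log-rule) area = 18 × (1 - 1/R)/ln R

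| R | Linear | True | Linear excess |
|---|---|---|---|
| 1.5 | 15.00 | 14.80 | +1.4% |
| 2 | 13.50 | 12.98 | +4.0% |
| 3 | 12.00 | 10.92 | +9.9% |
| 5 | 10.80 | 8.95 | +20.7% |

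These ratios correspond to terminal half-lives of about 30 h (R = 1.5, +1.4%), 18 h (R = 2, +4.0%) and shorter. If the decline has two phases, both rules overstate the segment, the log rule by less.

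**2. The whole AUC0-24 need not be high.** The curve is concave around the peak, where linear trapezoids run low. Take a first dose, one compartment, absorption 3 per h and half-life 30 h, so k = ln 2/30 = 0.0231 per h. Then C(t) = [3/(3 - k)] × (e^(-kt) - e^(-3t)), which peaks at 1.6 h.
- Values at 0, 1, 2, 4, 6, 24 h: 0, 0.935, 0.960, 0.919, 0.877, 0.579.
- 0 to 6 h: linear 5.089, true 5.310, difference -0.221.
- 6 to 24 h: linear 13.105, true 12.919, difference +0.186.
- Net: -0.035 on 18.230, or -0.2%.

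Linear-up/log-down on the same values gives -1.2%. Here the linear rule is slightly low and is also the closer of the two.

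**3. It can be well high.** Two compartments, half-life 30 h, absorption 1.5 per h, distribution rate 0.3 per h:

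| Rapid-phase weight | Profile | Linear | Linear-up/log-down |
|---|---|---|---|
| 0.7 | First dose | +9.9% | +5.9% |
| 0.7 | Steady state | +5.5% | +3.3% |
| 0.95 | First dose | +25.1% | +9.3% |
| 0.95 | Steady state | +19.4% | +9.7% |

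**4. Range over assumed curves.** One- and two-compartment oral curves were sampled at the protocol times and compared with fine-grid integration. Terminal half-life was 12 to 48 h, absorption 0.71 to 6 per h, distribution rate 0.15 to 1.0 per h and rapid-phase weight 0 to 0.95. Only curves whose true peak fell at 1 to 2 h were kept.

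| | First dose | Steady state |
|---|---|---|
| Linear error in AUC0-24 | about -1% to +32% | about 0% to +30% |
| Linear-up/log-down error | about -2% to +15% | about -2% to +12% |
| Linear below truth | about 11% of curves | none |
| Linear-up/log-down closer | about 81% | about 90% |

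The 6 to 24 h trapezoid supplied about 65% of linear AUC0-24 (range roughly 35% to 74%). The upper limits depend on grid spacing: a coarser grid over the same ranges gave +27.6% and +26.3% for the linear rule. The shares describe the grid, not patients.

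**5. CL/F.** If CL/F = dose/AUC over the same interval, an AUC error of +5% gives 1/1.05 - 1 = -4.8%, and +25% gives 1/1.25 - 1 = -20%. A first-dose CL/F based on AUC to infinity moves less. With a 30 h half-life and rapid absorption, the first 24 h hold about 1 - 2^(-24/30) = 43% of the total. A +10% error in AUC0-24 then adds only about 0.43 × 10% = 4.3%, leaving aside error in the extrapolated part.

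**The case against.** The strongest reply is that linear trapezoids are a recognized, fully specified option, so this is a preference between two standard settings. The size also rests on curves that the documents do not supply: for one-compartment curves at steady state with half-lives of 18 to 48 h, the linear error was only 0.02% to 2.2%. And the root cause is the missing sample, which a change of rule does not cure. All of this stands in part. It limits the point to a minor improvement, but it does not remove the usual upward bias.

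Four stronger readings are tempting and are not supported:
- **That linear trapezoids always overstate everolimus AUC.** This is true of the 6 to 24 h segment under a convex decline. It is not true of AUC0-24, as step 2 shows.
- **That the log rule is always closer.** It is closer in most assumed curves. Linear can win even at steady state: one compartment, absorption 4 per h and half-life 30 h gives +0.4% against -0.6%.
- **That CL/F is understated by the same proportion throughout.** That needs dose over AUC for the same interval, and Section 12.1.5 does not define the interval.
- **That the bias would be read as a drug interaction.** Section 12.1 gives shared P-glycoprotein transport as the reason for the PK work. But the comparison with single-agent trials in Section 12.1.5 is for eribulin, which is fitted by compartmental analysis and is untouched by this rule. No everolimus comparator is named, and both drugs are given on day 1, so no everolimus-alone profile exists within the trial.

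**Conclusion.** The point holds as a minor one. The stated rule and the stated schedule together put a single straight line across most of the dosing interval, on the falling part of the curve. The usual result is an overstated AUC0-24 and, at steady state, an understated CL/F. The size cannot be fixed from the documents: it runs from about zero, or slightly negative after a first dose, to about 30% over the assumed curves.

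The balance favors the change. Where linear was as close or closer, its own error was at most about 1.4%, and switching cost at most about 1.6 percentage points. Where linear-up/log-down was closer, it removed up to about 25 points. No primary endpoint, dose decision or stopping rule uses everolimus AUC. The conclusion assumes a peak at 1 to 2 h as in Section 1.2.2, a convex decline after 6 h and, for cycle 2, uninterrupted daily dosing beforehand.

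**What to change.** In Section 12.1.5, replace the integration rule for everolimus with: *linear-up/log-down trapezoids (linear while concentrations rise, logarithmic while they fall, and linear where the log rule cannot be computed, for example with equal or unquantifiable values)*. In the same sentence, state the AUC interval used for CL/F in each cycle.

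The cost is one sentence and a standard software setting, and it applies to samples already scheduled or collected. There are three small downsides:
- Some upward bias remains with a two-phase decline.
- In a minority of profiles the new rule is slightly less accurate.
- Comparison with published values obtained by the linear rule becomes less direct; reporting the linear AUC alongside deals with this.

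A whole-blood sample at 8 to 12 h would treat the cause more directly, but it needs an added draw. The 8 h research blood in Section 12.2.1 is not a ready substitute, because it depends on separate consent and uses tubes other than the EDTA tube specified for everolimus.

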12.1.6 Specimen collection/documentation

Prior to drug administration on day 1 of cycle 1 of treatment, an indwelling heparin lock should be placed so that serial specimens can be collected. At each sampling time, 1mL of blood will be drawn and discarded to assure that the solution used to maintain catheter patency does not dilute the sample. Even if a patient has a central venous catheter, it is preferable for the day 8 PK samples to be drawn through a peripheral heparin lock. However, if the patient objects or has problems with peripheral venous access, the central venous catheter may be used for PK sampling. In the event that the central venous catheter is used, sufficient blood should be withdrawn before each PK sample to assure that the solution used to maintain catheter patency does not dilute the PK sample. It is important to document whether the sample was collected through a heparin lock or central venous catheter, especially for day 1 sampling.

12.2 Molecular Studies

12.2.1 Blood collection

Blood collection will be performed from patients at the multiple time points for patients enrolled to expansion cohort (RP2D) and consented for additional blood collecton:

- Prior to the first dose of everolimus and eribulin.

- 4 hours, 8 hours after dose of everolimus and eribulin, on day 1, day 4 and day 8 of cycle 1.

A serum specimen for proteomic analysis will consist of 7ml of blood in an uncoated tube (collected in the red top). This procedure is performed under standard sterile medical conditions. The red tube should be kept at cold on wet ice (do not invert) and delivered within 15-30 minutes. Serum will be collected and stored at -80°C for proteomic analysis in [name] Laboratory using Luminex and mass spectrometry, with confirming ELISA, such as for VEGF, since everolimus and eribulin are known to influence angiogenesis.

A specimen for peripheral blood mononuclear cells (PBMC) and plasma collection will consist of 10ml of blood drawn into an ACD tube (yellow top). This tube will be kept at room temperature and inverted 5-10 times to prevent coagulation. The tube will be brought to a designated person/lab within 15-30 minutes. The processing and storage of these samples will follow the blood separation protocol established in [name] laboratory for the purpose of biomarker analyses as above. Lysates will be stored in aliquots at -80°C until analysis.

12.2.2 Skin punch biopsy

Two sets of optional skin punch biopsies (two biopsies per set for a total of four biopsies) will be performed for patients who enrolled to dose expansion cohort (Phase Ib, RP2d) and consented as follows:

- First set
 - Biopsy 1 (3mm diameter) will be performed one week prior to any dosing.
 - Biopsy 2 (3mm diameter) will be performed on the same site as Biopsy 1 on the day of the first dose of eribulin and everolimus; cycle 1 (prior to any dosing).
- Second set
 - Biopsy 3 (3mm diameter) will be performed on a new site on the day of the first dose of eribulin and everolimus; cycle 1 (prior to any dosing).
 - Biopsy 4 (3mm diameter) will be performed on the same site as Biopsy 3, one week later on the day that the second dose of eribulin is given (prior to dosing).

Skin biopsy specimen will be placed in formalin containers and transported to [name] lab for storage. Specimen will be analyzed for several biomarkers in epidermal and vascular tissue (see Section 12.2.4).

12.2.3 Tumor biopsy

Patient will be asked to provide a fresh tumor tissue from a newly obtained core or excisional biopsy of a tumor lesion upon study entry. Newly –obtained is defined as a specimen obtained up to 6 weeks (42 days) prior to initiation of treatment on day 1. Subjects for whom newly-obtained samples cannot be provided (e.g. inaccessible or subject safety concern) may submit an archived specimen only upon agreement from the study PI.

Tumors may be biopsied or resected at time of disease progression and will also be evaluated by proteomic analysis. Tumors for which frozen tissue can be obtained will be evaluated for breast cancer subtype using microarray analysis.

The tumors will be placed in snap frozen in liquid nitrogen and sent to [name] laboratory (see **Section 12.2.4**).

Protocol for Formaldehyde-Fixed, Paraffin Embedded Tissue Specimens That May Have Been or Biopsied or Resected Before, During, or After Treatment

Paraffin embedded specimens will be processed in conjunction with the routine duties of the COH Anatomic Pathology Department. Additional collection or storage of research specimens outside of the storage per clinical standard of care (which will include additional tissue biopsy cores or parts of surgical tissue specimens, not required for standard pathological diagnosis) will be allowed and conducted under this protocol.

Protocol Frozen Tissue Specimens That May Have Been or Biopsied or Resected Before, During, or After Treatment

Tissue collection will be performed on patients undergoing clinically indicated biopsies or surgical resection while at COH. Once the tissue is biopsied or surgically removed, the specimen will be taken to the pathology laboratory where the pathologist will ensure that the tissue is adequate for routine pathology analyses (diagnosis, margin status assessment, and other indicated purposes). Then, and only then, if excess tissue remains, samples of that tissue will be harvested for archiving in the tissue bank. This archival tissue will be divided and placed into vials, labeled with the subject's unique identification number (RPN) after all patient identifiers are removed, and flash-frozen in liquid nitrogen. It will then be placed into the City of Hope tissue bank freezer (located in the Department of Pathology/or if necessary due to storage space needs in the Pathology Core-tracked in the same data base/LIMS) at temperatures down to -80°C. This tissue will remain in the freezer for at least a one-month period of time, or longer if needed, to ensure that there is no additional diagnostic pathologic requirement for the frozen specimen. During this time, no analyses will be performed on the specimen. This period of time will be known as the “Fail-Safe” time period. The Fail-Safe time period is intended to allow the pathologists the opportunity to withdraw banked tissue for any additional diagnostic testing they determine is necessary to patient care. After the pathologist determines with final certainty, by the publishing of the official final

pathologic report, that there is no diagnostic pathologic requirement for the frozen specimen, then the archived specimen on that patient will be released for research analyses, under appropriate research protocol approved by the IRB.

Tissue collection for non-diagnostic/research purpose will preferably occur at the time of clinically indicated biopsies in the form of extra biopsy specimens. Alternatively, tissue collection for research purpose can occur under IRB-approved specific research protocols and after the patient signed the appropriate consent form. Patients, who are planning treatment with therapy prior to surgery, or have undergone definitive surgery, or are undergoing biopsy or removal of adjacent tissue or metastatic sites may be asked to consent to have an additional biopsy to collect pre-treatment or post-treatment tumor specimens for banking, or alternatively, allow for access tissue collection, such as lymph nodes, or other tissues (for example, brain metastasis).

These procurements can never compromise the establishment of proper diagnosis and the final say in allowing for such biopsies will reside with the pathologist.

In those patients who consent, the tissue collected at biopsy or in surgery, will be placed fresh frozen into the COH tissue bank freezer (located in the Department of Pathology/or if necessary due to storage space needs in the Pathology Core-tracked in the same data base/LIMS at temperatures down to -80°C. In addition, if samples are available, tissue will be also placed in a labeled plastic vial containing RNAlater™ (“RNAlater tissue protect tubes”, Ambien Inc. USA) and subjected to labeling, processing, and banking procedures as described above.

Protocol for Formalin-Preserved Tissue Specimens That May Have Been or Biopsied or Resected Before, During, or After Treatment

If any additional excess tissue remains, or procured during biopsy or surgery, samples of that tissue will be harvested for archiving in a formalin tumor bank in the department of Pathology. This archival tissue will be divided and placed into vials, labeled with the subject's unique identification number (RPN) after all patient identifiers are removed, and tissues will be released for research via IRB-approved protocols.

